6.3.3 Safety Analysis Set (SAS)

The SAS is defined as all participants who administered the medical device either in a site-supervised, proctor-supported, or unsupported setting. This analysis set will be used for summaries of safety data.

Statistical Analysis Plan (SAP)

Protocol: Phase 1 Study Evaluating Technologies for Point-of-Care Blood Collections in Support of Decentralized Outpatient Assessments in Pandemic and Clinical Trial Settings

Version Date: 27-Jun-2025

Sponsor: Resilience Government Services, Inc.

Protocol No: 5309/0024

7.0 Conventions and Derivations

7.1 Demographic and Baseline Characteristics

Age will be calculated as the number of years elapsed between birth date and the date of informed consent, adjusted for whether the birthday has passed as of the day of signing. (This corresponds to the typical calculation of age a person would use in conversation, namely, Age = floor ((Date of informed consent - date of birth)/365.25)).

BMI (kg/ m²) = weight (kg) / [height (m)]²

7.2 Derivation of Durations

Study day at visit: Date of interest – date of first clinic visit. One day is added if the difference is ≥ 0 .

Duration of events: End date of event - start date of event + 1

7.3 Handling of Missing Values

Partial medication dates will be imputed for the purposes of determining prior or concomitant status. Partial medication dates will be imputed as the earliest or latest date consistent with the partial start or end date, respectively. Completely missing medication start dates will not be imputed and those records will be categorized as concomitant in TFL summaries. Completely missing medication end dates will be assigned as "Ongoing" in TFL summaries.

Otherwise, missing data in this study will not be imputed.

8.0 Interim Analyses

No formal interim analysis will be performed.

9.0 Statistical Methods

All analyses will use SAS version 9.4 or higher. Standard summary statistics will be presented for continuous and discrete variables:

- Unless otherwise noted, categorical variables will be summarized using counts and percentages. Percentages will be rounded to one decimal place, except 100% which will be displayed without any decimal places, percentages will not be displayed for zero counts.
- Continuous variables will be summarized using the number of observations (n), mean, Standard Deviation (SD), median, minimum and maximum. The minimum and maximum values will be

Statistical Analysis Plan (SAP)

Protocol: Phase 1 Study Evaluating Technologies for Point-of-Care Blood Collections in Support of Decentralized Outpatient Assessments in Pandemic and Clinical Trial Settings

Version Date: 27-Jun-2025

Sponsor: Resilience Government Services, Inc.

Protocol No: 5309/0024

displayed to the same level of precision as the raw data, the mean, median, Q1, and Q3 to a further decimal place and the SD to two additional decimal places.

9.1 Subject Disposition

Subject disposition information will be summarized by cohort. The numbers and percentages of subjects enrolled/randomized, eligible and having used the medical device, terminated early, and the numbers and percentages of subjects who have completed the study and are eligible for analysis. The primary reasons for ineligibility and early withdrawal will also be tabulated.

The number and percentages of subjects in each analysis set will also be tabulated. A listing of each subject excluded from an analysis population will be listed as well as the reason why they were excluded from the population.

9.2 Demographic and Baseline Characteristics

Demographic characteristics (including age, sex, ethnicity, and race) and baseline characteristics (including height, weight, BMI, supine systolic and diastolic blood pressure, pulse, body temperature, and respiratory rate) will be summarized descriptively by Cohort for the Full analysis set.

Past medical history will be listed.

9.3 Treatments

9.3.1 Extent of Study Drug Exposure

There is no extent of study drug exposure for this study, however, counts and percentages of subjects using the TASSO+™ device with or without proctor supervision will be tabulated by cohort and visit using counts and percentages for the SAS.

9.3.2 Prior and Concomitant Medications

Prior and concomitant medications will be listed.

A medication will be defined as a prior medication if its start date is before the subject's date of first sample collection in the study.

A medication will be defined as a concomitant medication if its start date is on or after the subject's date of first sample collection in the study and prior to the date of the subject's last questionnaire response; if the subject does not have any questionnaire data, the medication start date must be prior to the subject's end of study participation date. If the medication start date comes after either of these dates, the medication will be categorized as poststudy.

Statistical Analysis Plan (SAP)

Protocol: Phase 1 Study Evaluating Technologies for Point-of-Care Blood Collections in Support of Decentralized Outpatient Assessments in Pandemic and Clinical Trial Settings

Version Date: 27-Jun-2025

Sponsor: Resilience Government Services, Inc.

Protocol No: 5309/0024

9.4 Important Protocol Deviations

The study specific Protocol Deviation Guidance Document defines all important protocol deviations.

Per ICON processes, important protocol deviations data will be entered into the system of record (ICOTrial).

The study team and the Sponsor will conduct on-going reviews of the deviation data from ICOTrial and the resulting set of evaluable subjects throughout the study, adjusting the deviation criteria as seems appropriate. The evaluable subjects set must be finalized at the post-freeze data review meeting (or earlier), prior to database lock.

The number of subjects excluded from the PPS and reasons for exclusion will be summarized by cohort and overall.

Numbers and percentages of subjects with protocol deviations will be summarized by category (important vs minor) and by cohort using the FAS population. Important protocol deviations leading to subject exclusions will be summarized in the final CSR.

9.5 Efficacy Analyses

9.5.1 Hypothesis Testing Strategy and Multiplicity

Hypothesis testing strategy and multiplicity are not applicable for this study.

9.5.2 Primary Endpoints

9.5.2.1 Sample Integrity

Descriptive statistics will be presented for the FAS and PPS to summarize the proportion of Tasso+™/SST and Tasso+™/EDTA samples collected on Day 1 for each cohort and on each of Days 29 and 57 for Cohorts A and B combined with the following attributes:

- Adequate volume, defined as at least 300 µL
- Without moderate or gross hemolysis, as defined by Central Laboratory SOP (see Table “Impact of Varying Degrees of Hemolysis” in [Section 6.3.1](#) of the protocol)
- Adequate volume and without moderate or gross hemolysis (for SST samples)
- Without clotting (for EDTA samples only)
- Adequate volume, without moderate or gross hemolysis, and without clotting (for EDTA samples only)

Sample integrity data will be analyzed using the laboratory vendor data for all subjects and visits with the exception of Cohort B Day 1 records, which were collected in the electronic data capture (EDC) system.

Statistical Analysis Plan (SAP)

Protocol: Phase 1 Study Evaluating Technologies for Point-of-Care Blood Collections in Support of Decentralized Outpatient Assessments in Pandemic and Clinical Trial Settings

Version Date: 27-Jun-2025

Sponsor: Resilience Government Services, Inc.

Protocol No: 5309/0024

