Establishing correlation coefficients of laboratory results collected by a study participant and compared to standard venipuncture will be an important milestone to rely solely on the patient/study participant to self-collect blood using either device/kit collected and to ship the samples to a designated laboratory. Indeed, in a recent study, even though Tasso/SST serum protein measurements were highly reproducible, self-collection at home with delayed sample processing was associated with significant concentration differences for several analytes compared to supervised, in-clinic collection with rapid processing ([Brandsma et al., 2022](#)). These results are to be compared to higher concordance results obtained among other studies focusing on serology: overall accuracy of 98.9% in the study conducted by [Hendelman et al., \(2021\)](#) and Cohen's kappa coefficient of 0.88 in the study conducted by [Wixted et al., \(2022\)](#).

The sample integrity of Tasso+™/SST (ie, adequate volume and absence of moderate or gross hemolysis) and Tasso+™/EDTA (ie, adequate volume, absence of moderate or gross hemolysis, and absence of clotting) capillary collection tubes will be evaluated on Day 1 for each cohort and on each of Days 29 and 57 for Cohorts A and B combined ([Table 4](#)).

Table 4 Sample Testing Table

Method of blood collection	Laboratory Results		Sample Integrity		
	SARS-CoV-2	Chemistry*	Sample Volume	Hemolytic Index	Clotting
Tasso+™ device	EDTA	✓	✓	✓	✓
	SST	✓	✓	✓	✓
Venipuncture	EDTA	✓			
	SST	✓	✓		

EDTA=ethylenediaminetetraacetic acid; SST=serum separator tube

Footnotes: Chemistry analytes include sodium, potassium, chloride, blood urea nitrogen, creatinine, glucose, phosphate, uric acid, and C-reactive protein.

There will be no complete blood count laboratory analysis using Tasso+™/EDTA capillary collection tube due to potential for red cell lysis and clotting, and insufficient blood volume collection that may preclude accurate results.

The impact of the timing of centrifugation after blood collection with Tasso+™ on blood sample integrity and accuracy will be evaluated on Day 1, as Tasso+™ blood samples of Cohort A participants will be centrifuged after shipping to the Central Laboratory, while Tasso+™ blood samples of Cohort B participants will be centrifuged and aliquoted by the Site prior to being shipped to the Central Laboratory alongside with venipuncture blood samples that will be centrifuged prior to shipping as per standard procedures.

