3 STUDY ENDPOINTS

3.1 Primary Endpoints

The primary endpoints that will be evaluated to assess the Tasso+™ blood collection device performance are as follows:

Sample integrity

- Percentage of overall Tasso+™/SST samples collected that are with adequate volume and without moderate or gross hemolysis on Day 1 for each cohort and on each of Days 29 and 57 for Cohorts A and B combined
- Percentage of overall Tasso+™/EDTA samples collected that are with adequate volume, without moderate or gross hemolysis, and without clotting on Day 1 for each cohort and on each of Days 29 and 57 for Cohorts A and B combined

Testing accuracy

- Correlation of SARS-CoV-2 serology between venipuncture and Tasso+™/SST or Tasso+™/EDTA samples on Day 1 for each cohort
- Correlation of each chemistry analyte between venipuncture and Tasso+™/SST samples on Day 1 for each cohort

Reliability

- Percentage of Tasso+™ device failures from Day 1 to Day 57 (see details in [Section 6.3.3](#)), defined as:
 - failure in activation of the lancet;
 - lack of any blood collection within 5 minutes;
 - incorrect attachment of the capillary collection tube to the device;
 - damage to the device or the capillary collection tube upon handling;
 - lack of maintained seal between the device and the skin surface of the participant; or
 - incomplete trigger of the button (not fully pressing the button once the Tasso+™ device is sealed to the skin surface).

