4.2 Steps to the Process

4.2.1 *Training*

Training will be provided on Days 1 and 29 and will include detailed IFU and online video training. The detailed IFU will be provided in a separate document, and an overview of IFU is provided in [Section 7.4](#). When administering the Tasso+™ remotely, participants will receive proctor-support from the Site on Day 29 (and as requested, on Day 57) during working hours, the intent being to guide the participant through the process and to help troubleshoot should any difficulties be encountered. Training on Day 57 should be performed only if it is specifically requested due to participant hesitation.

4.2.2 *Blood Collection*

Once trained, and by following the IFU provided (see [Section 7.4](#)), participants will self-administer the Tasso+™ device in the Clinic at the Investigator site (supervised) and subsequently remotely, ie, at home or a suitable remote location (proctor-supported on Day 29 and unsupported on Day 57). Self-collection may be additionally supported on Day 57 using a proctor session, as requested, to guide the participant through the process and help to troubleshoot any difficulties. The SST tube will be preferably collected from the left upper arm and the EDTA tube will be preferably collected from the right upper arm.

As per IFU, participants will have to gently invert the Tasso+™ capillary collection tubes after the full collection process is completed.

4.2.3 *Blood Volume and Clotting Analyses*

Blood volume and clotting analyses will be assessed before centrifugation. Thus, for Cohort B, on Day 1, these endpoints will be assessed by the Site, while for Cohort A, on Day 1 and for Cohorts A and B combined on Days 29 and 57, these endpoints will be assessed by the Central Laboratory (see [Section 6.3](#)).

4.2.4 *Centrifugation*

Tasso+™ blood samples of participants randomized to Cohort A, collected on Day 1, will be centrifuged upon receipt by the Central Laboratory, as per the real-world use of Tasso+™.

Tasso+™ blood samples of participants randomized to Cohort B, collected on Day 1, will be centrifuged and aliquoted by the Site before shipping, following the same procedure as for venipuncture blood samples.

Tasso+™ blood samples of participants from both Cohorts A and B, collected on Days 29 and 57, will be centrifuged upon receipt by the Central Laboratory, as per the real-world use of Tasso+™.

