Thus, for Cohort B, on Day 1, centrifugation and aliquoting will be performed by the Site, while for Cohort A, on Day 1 and for Cohorts A and B combined on Days 29 and 57, centrifugation and aliquoting will be performed by the Central Laboratory.

4.2.5 *Shipping*

On Day 1, Tasso+™ and venipuncture collection tubes will both be shipped by the Site following this visit.

On Days 29 and 57, blood will be shipped by the participant (remotely proctor-supported and unsupported, respectively).

4.2.6 *Hemolysis Analysis*

Hemolytic index will be assessed before testing by the Central Laboratory (see [Section 6.3](#)).

4.2.7 *Testing*

Upon receipt, both SST and EDTA samples will be tested by Central Laboratory (see [Section 6.3](#)).

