7.2 Blinding

This is an open-label study. Participants, HCPs, and laboratory technicians will not be blinded to the study intervention.

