9.5.4.5 Summary of Collected Sample Volume

Boxplots will be produced to visualize the volume of sample collected for each subject by time point and collection method (SST or EDTA). The x-axis of the boxplot will be split by cohort (for Day 1 only), with two boxplots for each cohort (one for SST and one for EDTA). Day 29 and Day 57 boxplots will summarize all subjects combined, with one boxplot for SST and one boxplot for EDTA. The figure will be produced for the PPS.

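### Does the change of reader between cohorts on Day 1 (Site in B, Central Laboratory in A) require a change to the sample integrity analysis?

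*SAP*

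**What the plan says.** Protocol 4.2.3 sets the stage of reading: "Blood volume and clotting analyses will be assessed before centrifugation". It then assigns the readers: "for Cohort B, on Day 1, these endpoints will be assessed by the Site", while the Central Laboratory reads Cohort A on Day 1 and both cohorts on Days 29 and 57. Protocol 4.2.4 has Cohort A's Day 1 tubes spun on receipt at the Central Laboratory and Cohort B's spun and aliquoted at the Site before shipping. For hemolysis, Protocol 4.2.6 makes no cohort exception: "Hemolytic index will be assessed before testing by the Central Laboratory".

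SAP 9.5.2.1 lists volume, hemolysis, clotting (EDTA only) and the composites, by cohort on Day 1 and combined on Days 29 and 57. Its data-source rule is laboratory vendor data "with the exception of Cohort B Day 1 records, which were collected in the electronic data capture (EDC) system". The by-cohort Day 1 layout follows the primary endpoint in Protocol 3.1, which for EDTA samples asks for the share with adequate volume, "without moderate or gross hemolysis, and without clotting on Day 1 for each cohort".

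The purpose of the cohort contrast appears in Protocol 1.2, which says that the impact of centrifugation timing "on blood sample integrity and accuracy will be evaluated on Day 1".

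**The concern.** Read together, these sections seem to set the cohort comparison a question that two of the three integrity components cannot cleanly answer. When volume and clotting are read, no tube in either cohort has been spun. The cohorts differ at that moment in reader, place and time since collection. The study is open-label; Protocol 7.2 says that "laboratory technicians will not be blinded to the study intervention". If Sites and the laboratory read differently, a by-cohort difference in a primary endpoint could come from the reading alone and be reported as an effect of centrifugation timing.

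The SAP's data-source sentence adds two smaller doubts. It names no component, so taken literally it would draw Cohort B's Day 1 hemolysis from EDC, although that is a Central Laboratory result. It also sits awkwardly with Protocol 4.1, 6.3.1 and 9.4.1.1 and SAP 6.0, which assign volume, clotting or integrity in general to the Central Laboratory without an exception for Cohort B.

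**Working it through.** **Allocation.** 200 × 2/3 = 133.3 and 200 × 1/3 = 66.7, which reproduces the planned 133 and 67. The Site-read share of Day 1 tubes of each type is 67/200 = 33.5%.

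**Who reads what on Day 1** (Protocol 4.2.3, 4.2.4, 4.2.6):

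| Component | Cohort A | Cohort B | What differs between cohorts |
|---|---|---|---|
| Volume | Central Laboratory, after shipping, unspun | Site, before shipping, unspun | Reader, place, elapsed time; not centrifugation |
| Clotting (EDTA) | Central Laboratory, after shipping, unspun | Site, before shipping, unspun | Time unspun, plus reader and place |
| Hemolytic index | Central Laboratory; tube spun there after shipping | Central Laboratory; tube spun at the Site | Time unspun, plus who spins, where, and whether a tube or an aliquot is shipped |

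Three things follow.

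1. By-cohort volume carries no information on centrifugation timing.
2. For clotting, the longer unspun wait in Cohort A is part of what randomization varies. Only reader and place are confounded with it.
3. Hemolysis has a single reader but is not a clean timing contrast either, because the operator and the shipped form also change.

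**Possible size, volume.** Protocol 6.3.1 gives 250–500 µL for EDTA kits and an adequacy cut-off of 300 µL. Assume volumes spread evenly over that range, with a reading offset d in Cohort B. The adequate share is (500 − (300 − d))/250:

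- d = 0: 200/250 = 80.0%
- d = ±10 µL: 84.0% or 76.0%
- d = ±25 µL: 90.0% or 70.0%

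The standard error of the cohort difference at 80% is √(0.8 × 0.2 × (1/67 + 1/133)) = 0.0599, so the 95% half-width is 1.96 × 5.99 = 11.7 points. Shifts of 4 and 10 points lie inside it. The SST kit range starts at 400 µL, so within that range an offset of up to 100 µL would change nothing. The range is nominal, however, and Protocol 1.1.3 reports some insufficient collections.

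**Possible size, clotting.** Assume that 10% to 50% of EDTA tubes are clotted in both cohorts and that the Site fails to record 10% to 30% of these. The upper value of 50% echoes the share seen with an earlier device generation and another tube type in Protocol 1.1.3. The no-clotting rate then differs by 0.10 × 0.10 = 1 point up to 0.50 × 0.30 = 15 points.

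For the EDTA composite, take adequate volume at 70% to 93.4% (the range of collection success in the two published studies in Protocol 1.2), assume 10% moderate or gross hemolysis, and treat components as independent. The smallest difference is 0.70 × 0.90 × (0.910 − 0.900) = 0.6 points. The largest is 0.934 × 0.90 × (0.650 − 0.500) = 12.6 points. The composite half-widths run from about 12 to 15 points. Only the extreme clotting case reaches its own half-width: 15 points against 1.96 × √(0.50 × 0.50/133 + 0.65 × 0.35/67) = 14.2 points.

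**What a change would alter.** The SAP specifies no test, interval or model for the cohort difference (9.5.1 states that hypothesis testing does not apply). The by-cohort proportions would be computed from the same readings whether or not the text named the reader. Days 29 and 57 are unaffected, since the Central Laboratory reads both cohorts.

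**The case for a change.** The strongest case for changing the SAP is that the protocol's rationale invites the timing interpretation, Day 1 integrity by cohort is a primary endpoint, and a sentence or two would cost almost nothing. Without it, a report author might ascribe to centrifugation a difference that arose from who read the tube. The scenarios above show that such a difference need not be trivial if the readers disagree markedly. The facts in this case stand, and so does a caveat: volume should not be interpreted as a timing effect, and clotting and the composites should be interpreted with the change of reader in mind.

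It does not carry through to a change in the plan. The only link to centrifugation timing is one sentence of rationale; the objectives and endpoints do not mention it, and the SAP draws no such inference. The split is also close to unavoidable: volume and clotting must be read before spinning, and Cohort B's tubes are spun at the Site, so the Central Laboratory never receives them unspun. Protocol 4.2.3 tells any report author who read what.

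A stronger instruction would overcorrect. Barring attribution for clotting would set aside the waiting time that randomization varies. Relying on hemolysis alone would ignore the change of operator and shipped form. Nor could the Day 1 volume boxplots in SAP 9.5.4.5 serve as a check on reader agreement: they show different participants, each tube read once, and are limited to a per-protocol set requiring at least five successful administrations.

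On the data source, an analyst who knows Protocol 4.2.6 will take the hemolytic index from the Central Laboratory result. If EDC held no such value, Cohort B's hemolysis row would come out empty and the slip would be obvious. The general statements naming the Central Laboratory are carry-over wording. They should be reconciled with 4.2.3 if the documents are reopened, but the specific section and the SAP's EDC rule agree with each other.

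**Conclusion.** The reader split is real and limits interpretation: by-cohort Day 1 volume says nothing about centrifugation timing, and by-cohort clotting and the composites mix time unspun with a change of reader and place. It affects 33.5% of Day 1 tubes of each type. Under assumed reading differences, the induced shift in the EDTA composite from clotting is 0.6 to 12.6 points, and the shift in EDTA volume adequacy is 4 to 10 points. No agreement data in the documents show that any such difference exists.

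No change to the plan follows. The analysis is descriptive, the timing question is in no objective or endpoint, the readers are already stated in Protocol 4.2.3, and naming them again in the SAP would alter no computed result. This rests on one assumption: that Cohort B's Day 1 hemolysis comes from the Central Laboratory, as Protocol 4.2.6 implies. What remains is a point of care for whoever writes the report's discussion of the Day 1 cohort results.
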